1.2.3. Clinical Studies of GS-5718

GS-US-451-5399: This is an ongoing, first-in-human (FIH), Phase 1 study in healthy volunteers to evaluate the safety, tolerability, and pharmacokinetics (PK) of GS-5718 and the effect of food and acid-reducing agents on GS-5718 PK.

1.2.3.1. Clinical Safety

As of November 20, 2020, GS-5718 has been administered to 62 healthy subjects in the FIH study.

GS-5718 in tablet form has been administered to healthy male and female subjects in single ascending doses (up to 150 mg; Part A: Cohorts 1-3 of GS-US-451-5399) and multiple ascending oral doses (up to 150 mg) for 10 days (Part C: Cohorts 6-8 of GS-US-451-5399). Part B of GS-US-451-5399 (Cohort 5) examined food effect and the potential for drug interactions with GS-5718 and a representative acid-reducing agent (omeprazole) with 50 mg single doses of GS-5718. Due to the ongoing nature of the study, it remains blinded to study subjects and the investigator but is unblinded to limited team members of the study sponsor.

GS-5718 has been well tolerated thus far during this study. No deaths, serious treatment-emergent adverse events (TEAEs), or TEAEs leading to study drug discontinuation were reported during the 6 months of the study. There have been no clinically relevant electrocardiogram (ECG) or vital sign abnormalities. When dosed with a single dose of GS-5718 at 150 mg, 1 subject experienced 2 TEAEs (headache and dyspepsia). Both events were Grade 1 in severity. When dosed with multiple doses of GS-5718 at 150 mg daily, 1 subject experienced 2 TEAEs (constipation and maculo-papular rash). The maculo-papular rash was related to the electrodes used for the ECG. Both events were Grade 1 in severity. All TEAEs were self-limited. There were no Grade 3 or 4 TEAEs in any cohorts of this study (Table 1-1).

All treatment emergent laboratory abnormalities are summarized in Table 1-2. There were no Grade 3 or 4 treatment emergent laboratory abnormalities associated with single or multiple administrations of the 150 mg dose. There have been 4 treatment emergent laboratory abnormalities of Grade 3 or higher in any cohort. One subject in Cohort 2 (50 mg single dose) experienced a Grade 3 elevation of creatine kinase (CK) following discharge from the clinic (follow-up visit on Day 12). The subject was asymptomatic. The investigator attributed the elevated CK levels to strenuous exercise reported by the subject. No specific intervention was required. A recheck of CK levels at an unscheduled visit 3 days later (Day 15) showed a trend toward normalization. One subject in Part B of the study (Cohort 5) experienced Grade 3 neutropenia on Day 11 and Day 19. This subject was also noted to have low-normal absolute neutrophil counts (ANC) prior to dosing both at screening and admission (1.67×10^9 cells/mL and 2.02×10^9 cells/L respectively). Two subjects in Cohort 5 experienced Grade 3 CK elevations after discharge on follow-up (Day 30), which the investigator attributed to activity. No specific interventions were required and a recheck of CK levels on unscheduled visits showed a trend toward normalization in both cases.

One subject in Cohort 7 met protocol specified stopping criteria based on a plasma thiocyanate level $> 200 \mu\text{mol/L}$. The results from a repeat analysis of the sample as well as additional unscheduled collections were all below the protocol-specified stopping criteria limit of $200 \mu\text{mol/L}$. There were 2 additional subjects with a plasma thiocyanate level $> 200 \mu\text{mol/L}$ that were detected following administration of study drug. This occurred in 1 subject in Cohort 6 on Day 9 (GS-5718 15 mg or PBO) and in another subject in Cohort 8 on Day 1 (GS-5718 150 mg or PBO). Retesting of the same sample (subject in Cohort 6) or from a backup sample collected at the same time (subject in Cohort 8) showed a plasma retest thiocyanate level below $200 \mu\text{mol/L}$. Neither subject discontinued study drug; available data from this study remains blinded.

Collectively, results from the GS-US-451-5399 healthy volunteer study indicates that GS-5718 is generally well tolerated at the doses explored to date.

Table 1-1. GS-US-451-5399 Treatment-Emergent Adverse Events: Overall Summary

Number (%) of Subjects with Any	Cohort 1 15 mg SAD (N=10)	Cohort 2 50 mg SAD (N=10)	Cohort 3 150 mg SAD (N=10)	Cohort 5 50 mg Food/PPI (N=14)	Cohort 6 15 mg MAD (N=10)	Cohort 7 50 mg MAD (N=10)	Cohort 8 150 mg MAD (N=10)	Total (N=74)
TEAE	1 (10.0%)	3 (30.0%)	1 (10.0%)	6 (42.9%)	4 (40.0%)	3 (30.0%)	1 (10.0%)	19 (25.7%)
TEAE with Grade 3 or Higher	0	0	0	0	0	0	0	0
TEAE with Grade 2 or Higher	0	0	0	1 (7.1%)	0	0	0	1 (1.4%)
TEAE Related to Study Drug	0	0	0	4 (28.6%)	0	2 (20.0%)	0	6 (8.1%)
TEAE Related to Study Drug with Grade 3 or Higher	0	0	0	0	0	0	0	0
TEAE Related to Study Drug with Grade 2 or Higher	0	0	0	1 (7.1%)	0	0	0	1 (1.4%)
TE Serious AE	0	0	0	0	0	0	0	0
TE Serious AE Related to Study Drug	0	0	0	0	0	0	0	0
TEAE Leading to Premature Discontinuation of Study Drug	0	0	0	0	0	0	0	0
TEAE Leading to Premature Discontinuation of Study	0	0	0	0	0	0	0	0
All Deaths	0	0	0	0	0	0	0	0
TEAE Leading to Death	0	0	0	0	0	0	0	0

AE = adverse event; MAD = multiple ascending dose, PPI = proton pump inhibitor; SAD = single ascending dose; TEAE = treatment-emergent adverse event

Table 1-2. GS-US-451-5399 Treatment-Emergent Laboratory Abnormalities: Overall Summary

Maximum Postbaseline Toxicity Grade	Cohort 1 15 mg SAD (N=10)	Cohort 2 50 mg SAD (N=10)	Cohort 3 150 mg SAD (N=10)	Cohort 5 50 mg Food/PPI (N=14)	Cohort 6 15 mg MAD (N=10)	Cohort 7 50 mg MAD (N=10)	Cohort 8 150 mg MAD (N=10)	Total (N=74)
Subjects with Postbaseline Value	10	10	10	14	10	9	10	73
Grade 3 or 4	0	1 (10.0%)	0	3 (21.4%)	0	0	0	4 (5.5%)
Grade 3	0	1 (10.0%)	0	3 (21.4%)	0	0	0	4 (5.5%)
Grade 4	0	0	0	0	0	0	0	0
Neutrophils (Decreased)								
Grade 3 or 4	0	0	0	1 (7.1%)	0	0	0	1 (1.4%)
Grade 3	0	0	0	1 (7.1%)	0	0	0	1 (1.4%)
Grade 4	0	0	0	0	0	0	0	0
Creatine Kinase (Increased)								
Grade 3 or 4	0	1 (10.0%)	0	2 (14.3%)	0	0	0	3 (4.1%)
Grade 3	0	1 (10.0%)	0	2 (14.3%)	0	0	0	3 (4.1%)
Grade 4	0	0	0	0	0	0	0	0

MAD = multiple ascending dose, PPI = proton pump inhibitor; SAD = single ascending dose;

1.2.3.2. Pharmacokinetic Profile

Following single-dose administration of 15, 50, or 150 mg GS-5718 under fasting conditions, GS-5718 was absorbed rapidly with the maximum plasma concentration (C_{max}) occurring between 0.75 to 2 hours after dosing (median T_{max}). Following multiple-dose administration of 15, 50, or 150 mg once daily under fed conditions (standard breakfast), the median T_{max} ranged from 3 to 4 hours. Across the dose levels evaluated, GS-5718 exhibited a median $t_{1/2}$ of 25 to 33 hours following single and multiple doses. GS-5718 exposure (AUC and C_{max}) increased in an approximately dose proportional manner across the range of 15 mg to 150 mg. Consistent with the elimination half-life, GS-5718 exposure (AUC and C_{max}) accumulated following multiple, once-daily doses (1.6 to 2.4-fold for AUC and 1.5 to 2.5-fold for C_{max}). Steady-state appears to have been reached by Day 5 to 7.

Administration of GS-5718 with food (high-fat/high-calorie meal) resulted in delayed GS-5718 T_{max} (from 1 to 4 hours) with an approximately 18% reduction in mean C_{max} and no change in mean AUC. Omeprazole (with a 5-day pretreatment at 40 mg once daily dose) reduced mean C_{max} and AUC of GS-5718 by approximately 42% and 22%, respectively, with no change in the T_{max} of GS-5718.

1.2.3.3. Pharmacodynamic Profile

Pharmacodynamics were assessed measuring changes in ex vivo stimulated (TLR7/8, R848) secretion of TNF- α . Several cytokines were evaluated and TNF- α was chosen as primary PD parameter. Preliminary results in changes in TNF- α levels, as measured by the primary PD parameters (AUC_{0-24} , and $\% \Delta T_{max\% \Delta}$) were determined to be sensitive measures of changes in TNF- α after single dose administration of placebo, 15, 50, or 150 mg GS-5718 under fasting conditions and 50 mg under fed conditions in healthy subjects (Table 1-3). GS-5718 significantly decreased TNF- α AUC_{0-24} and inhibited TNF- α secretion measured as percentage change of TNF- α levels from baseline to 1 hour and to 24-hours postdose compared to placebo. Administration of 50 mg GS-5718 with food did not result in a significant prolonged time to reach $\% \Delta T_{max}$ compared to administration of 50 mg GS-5718 under fasting conditions (Table 1-3).

Table 1-3. GS-US-451-5399 Preliminary Pharmacodynamic Parameters (inhibition of ex vivo [TLR7/8, R848] stimulated TNF- α) Following Single-Dose Administration of Placebo, or GS-5718 Under Fasting or Fed Conditions in Healthy Subjects

		Placebo	GS-5718			
			Single Dose (SAD, FE)			
		Fasted	15 mg Fasted	50 mg Fasted	50 mg Fed	150 mg Fasted
TNF- α	AUC_{0-24hr} geometric mean (% CV)	16392 (29.5)	2127 (39.4)***	757 (62.0)***	828 (62.3)***	614 (70.9)***
	$T_{max} \% \Delta$	3.46 (129)	1.30 (82.4)*	4.15 (206)	3.75 (129)	5.62 (281)
	$\% \Delta T_{max \% \Delta}$	-12.8 (-24.8, -0.816)	-97.2 (-98.0, -96.4)***	-97.3 (-98.2, -96.4)***	-97.9 (-99.0, -96.7)***	-98.1 (-100.1, -96.1)***
	$\% \Delta$ at 1-hour postdose	19.1 (-3.65, 41.9)	-96.7 (-98.0, -95.5)***	-95.9 (-97.5, -94.3)***	-88.1 (-97.2, -79.0)***	-96.7 (-100.2, -93.3)***
	$\% \Delta$ at 24-hours postdose	13.5 (-13.1, 40.1)	-84.9 (-90.5, -79.4)***	-95.0 (-96.3, -93.7)***	-96.2 (-97.4, -95.0)***	-96.1 (-99.7, -92.5)***

FE = food effect; SAD = single ascending dose; TNF = tumor necrosis factor

$AUC_{(0-24hr)}$ and T_{max} are reported as geometric mean, % CV

$\% \Delta T_{max \% \Delta}$, $\% \Delta$ at 1-hour postdose, $\% \Delta$ at 24-hours postdose are reported as mean, 95% CI

$AUC_{(0-24hr)}$ is the average AUC of the normalized values from baseline to 24-hours postdose.

$T_{max \% \Delta}$ is the time in hours postdose of maximum percent change from baseline value.

$\% \Delta T_{max \% \Delta}$ is the maximum percentage change from baseline value.

*Indicates P-Value < 0.05 from Wilcoxon rank-sum test for the treatment when compared to placebo. **Indicates P-value < 0.01,

***Indicates P-value < 0.001

1.3. Rationale for the Study

GS-5718 is an inhibitor of IRAK4, a serine/threonine kinase at the top of the signaling cascade for TLR and IL-1R mediated inflammatory responses. TLRs are activated via pathogen-associated molecular patterns (PAMPs) and damage-associated molecular patterns (DAMPs) that initiate downstream immune responses. Dysregulated signaling through TLRs and IL-1R can drive uncontrolled immune cell activation and chronic inflammation. This inflammatory state is associated with multiple chronic inflammatory and autoimmune diseases, including SLE and CLE.

Nonclinical studies have revealed a critical role for TLR7 and IRAK4 in murine lupus. TLR7-deficient and IRAK4 kinase inactive knock-in mice have been shown to be protected against the development of lupus-like murine disease {Murphy 2017}. Plasmacytoid dendritic cells isolated from these IRAK4 knock-in mice are completely resistant to TLR7 and TLR9-induced secretion of IFN- α {Kim 2007}. In the in vivo NZB/W preclinical lupus model, GS-5718 statistically improved survival, histologic renal parameters and measures related to lupus activity. GS-5718 also returned PD measures toward predisease levels.

Evidence supports a role for IRAK4 signaling in human studies. The peripheral interferon-stimulated gene signature observed in SLE patients is considered to be TLR7- and TLR9-dependent. Human pDC produce the majority of type I interferons, in particular in response to TLR7 or TLR9 agonism. In in vitro cellular assays, GS-5718 inhibited TLR7- and TLR9-stimulated production of IFN- α in primary human pDC and human whole blood. In human PBMCs, GS-5718 inhibited TLR7-stimulated expression of a 4 gene type I interferon-stimulated gene panel (IFI27, IFI44, IFI44L, and RSAD2). GS-5718 also inhibited IFN- α and TNF- α production from pDC stimulated with sera from patients with SLE.

1.4. Rationale for the Study Design

The goal of this Phase 1b study is to evaluate the safety of GS-5718 over 4 weeks in a population of subjects with CLE with or without SLE. The generated data will inform target engagement and safety in the LE population, which can further inform future studies. CCI

Nonclinical toxicology data support dosing of 115 mg once daily. Nonclinical pharmacology data shows that GS-5718 is a potent and selective inhibitor of IRAK4. In a Phase 1 healthy volunteer study, GS-5718 was generally well tolerated. At all dose levels of GS-5718 studied (15 mg, 50 mg, and 150 mg), there were no serious adverse events (SAEs), TEAEs leading to study drug discontinuation, clinically significant ECG/vital sign abnormalities, or deaths.

Available evidence supports proceeding with a Phase 1b evaluation of GS-5718 in subjects with CLE to assess for safety and tolerability at 1 month.

1.5. Rationale for Dose Selection of GS-5718

This study will evaluate the safety and tolerability of 115 mg once daily GS-5718 for 4 weeks in subjects with CLE. The dose was selected based on short-term safety, PK, and PD results from Study GS-US-451-5399 in healthy subjects. This dose is expected to be well tolerated. Based on Phase 1 PK/PD data, the 115 mg dose is predicted to be above EC₉₀ for TNF- α inhibition, a peripheral biomarker for PD response. This dosing regimen is further supported by the 4-week preclinical toxicology studies. In addition to expected safety and tolerability, GS-5718 has demonstrated efficacy in the NZB/W model of spontaneous murine lupus. Taken together, these data support the evaluation of GS-5718 115 mg once daily in subjects with CLE.

1.6. Risk/Benefit Assessment for the Study

There remains a high unmet need for efficacious and safe treatment options for patients with lupus. This Phase 1b study will characterize the safety and tolerability of GS-5718 in this disease state while also establishing the effect of IRAK4 inhibition on clinical outcomes. Based on the clinical data to date, as well as the data from nonclinical efficacy and mechanistic studies, clinical investigation of GS-5718 in patients with lupus is warranted. Safety data from the clinical study available for GS-5718 suggest an acceptable benefit-risk ratio at the proposed 115 mg once daily dose. Furthermore, use of a sponsor-unblinded trial design will permit ongoing monitoring of each subject's clinical status, laboratory values, and reported adverse events (AE).

An infectious disease pandemic may pose additional risks to study drug availability, study visit schedule, and adherence to protocol-specified safety monitoring or laboratory assessments. Refer to [Appendix 2](#) for further details on the risks and risk mitigation strategy.

1.7. Compliance

This study will be conducted in compliance with this protocol, Good Clinical Practice (GCP), and all applicable regulatory requirements.

2. OBJECTIVES

The primary objective of this study is as follows:

- To evaluate the safety and tolerability of GS-5718 in subjects with CLE with or without SLE

The secondary objective of this study is as follows:

- To characterize the PK of GS-5718 in subjects with CLE with or without SLE

The exploratory objectives of this study are as follows:

3. STUDY DESIGN

3.1. Endpoints

The primary endpoints of this study are as follows:

[figure not shown]
- Number of subjects that experience AEs
- Number of subjects that experience laboratory abnormalities

The secondary endpoint of this study is as follows:

- PK parameters of GS-5718, including AUC_{τ} and C_{\max}

The exploratory endpoints of this study are as follows:

3.2. Study Design

This is a Phase 1b, multicenter, randomized, blinded, placebo-controlled, 4-week study evaluating the safety and tolerability of GS-5718 in subjects with CLE.

A schematic of this study is provided in [Figure 3-1](#).

Figure 3-1. Study Schema

3.3. Study Treatments

Eligible subjects, continuing their standard of care therapy, will be randomized in a 2:1 blinded fashion to 1 of 2 arms. The first being 115 mg GS-5718 once daily in addition to standard of care (approximately 8 subjects). The second being placebo-to-match (PTM) GS-5718 once daily in addition to standard of care (approximately 4 subjects).

3.4. Duration of Treatment

Randomized subjects will receive GS-5718 or PTM GS-5718 for a maximum of 4 weeks.

3.5. Discontinuation Criteria

3.5.1. Study Drug Interruption

The sponsor medical monitor should be consulted prior to study drug interruption, when medically feasible.

Prior to resuming study drug, the investigator should discuss the case with the sponsor medical monitor.

Study drug interruption should be considered in the following circumstances:

- Intercurrent illness that would, in the judgment of the investigator, affect assessments of clinical status to a significant degree.
- If the subject has any signs or symptoms suggestive of systemic infection, study drug dosing should be interrupted per the judgment of the investigator. Any subject who develops a new infection during the study should undergo prompt and complete diagnostic testing appropriate for an immunocompromised individual, and the subject should be closely monitored. Study drug should continue to be paused until the subject's event has resolved, per investigator judgment.

3.5.2. Study Drug Discontinuation Criteria

The sponsor medical monitor should be consulted prior to study drug discontinuation, when medically feasible.

Study drug should be permanently discontinued in the following circumstances:

- Any opportunistic infection
- Any Grade 2 or higher cardiovascular or hematologic event (or Grade 3 lymphopenia or anemia as described below under "Laboratory Criteria")
- Any serious infection that requires antimicrobial therapy or hospitalization, or any infection that meets SAE reporting criteria
- Unacceptable toxicity, or toxicity that, in the judgment of the investigator, compromises the subject's ability to continue study-specific procedures or is considered to not be in the subject's best interest
- Subject request to discontinue for any reason
- Subject noncompliance, per investigator judgment
- Investigator discretion
- Female subject becomes pregnant during the study
 - NOTE: If the female partner of a male subject becomes pregnant during the study, the investigator, in consultation with the Gilead medical monitor, will determine whether the subject should continue in the study on a case-by-case basis.
- Discontinuation of the study at the request of the study sponsor, a regulatory agency or an institutional review board (IRB)/independent ethics committee (IEC)

- Subject use of prohibited concurrent systemic therapy
- An absolute QTcF > 500 msec or a change from the baseline QTcF value > 60 msec
- Laboratory Criteria: After becoming aware of any of the abnormal laboratory values below, study drug should be paused, and an unscheduled visit (ie, sequential visit) should occur to retest within 3 to 7 days (except creatinine, which should be retested 7 to 14 days apart). Retest may be obtained sooner if medically indicated, per investigator judgment.
- If the laboratory abnormality is confirmed by the retest, then study drug should be permanently discontinued.
 - Hemoglobin < 8.0 g/dL (International System of Units [SI]: < 80.0 g/L)
 - ANC < 1500 cells/mm³ (SI: < 1.5 × 10⁹ cells/L)
 - Lymphocyte count < 500 cells/mm³ (SI: < 0.5 × 10⁹ cells/L)
 - Platelet count < 75,000 cells/mm³ (SI: < 75 × 10⁹ cells/L)
 - Any AST and/or ALT ≥ 3 × ULN independent of signs of liver damage
 - Estimated CL_{cr} < 60 mL/min based on the Cockcroft-Gault equation

Subjects who discontinue study drug dosing at any time should continue with study visits, procedures, and assessments, if deemed medically appropriate by the investigator. Subjects who permanently discontinue study drug for any reason may be replaced (see Section 4.1.1 for more details).

Subjects withdrawing from the study should complete the early termination (ET) and follow-up (FU) visits. Subjects are free to withdraw from the study at any time without providing reason(s) for withdrawal and without prejudice to further treatment. The reason(s) for withdrawal will be documented in the electronic case report form (eCRF).

Reasonable efforts will be made to contact subjects who are lost to follow up. All contacts and contact attempts must be documented in the subject's file.

The sponsor has the right to terminate the study at any time in case of safety concerns or if special circumstances concerning the study medication or the company itself occur, making further treatment of subjects impossible. In this event, the investigator(s) and relevant authorities will be informed of the reason for study termination.

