7.5. Gilead Reporting Requirements

Depending on relevant local legislation or regulations, including the applicable US FDA Code of Federal Regulations, the EU Clinical Trials Directive (2001/20/EC) and relevant updates, and other country-specific legislation or regulations, Gilead may be required to expedite to worldwide regulatory agencies reports of SAEs which may be in the form of line listings, serious adverse drug reactions, or suspected unexpected serious adverse reactions (SUSARs). In accordance with the EU Clinical Trials Directive (2001/20/EC), Gilead or a specified designee will notify worldwide regulatory agencies and the relevant IEC in concerned Member States of applicable SUSARs as outlined in current regulations.

Assessment of expectedness for SAEs will be determined by Gilead using reference safety information specified in the IB or relevant local label as applicable.

All investigators will receive a safety letter notifying them of relevant SUSAR reports associated with any study drug. The investigator should notify the IRB or IEC of SUSAR reports as soon as is practical, where this is required by local regulatory agencies, and in accordance with the local institutional policy.

7.6. Clinical Laboratory Abnormalities and Other Abnormal Assessments as Adverse Events or Serious Adverse Events

Laboratory abnormalities without clinical significance are not to be recorded as AEs or SAEs. However, laboratory abnormalities (eg, clinical chemistry, hematology, urinalysis) that require medical or surgical intervention or lead to study drug interruption, modification, or discontinuation must be recorded as an AE, as well as an SAE, if applicable. In addition, laboratory or other abnormal assessments (eg, ECG, X-rays, vital signs) that are associated with signs and/or symptoms must be recorded as an AE or SAE if they meet the definition of an AE or SAE as described in Sections 7.1.1 and 7.1.2. If the laboratory abnormality is part of a syndrome, record the syndrome or diagnosis (eg, anemia), not the laboratory result (ie, decreased hemoglobin).

Severity should be recorded and graded according to the CTCAE. For AEs associated with laboratory abnormalities, the event should be graded on the basis of the clinical severity in the context of the underlying conditions; this may or may not be in agreement with the grading of the laboratory abnormality.

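### Does Protocol 3.5.2 leave open whether a low neutrophil or platelet count that is normal on retest ends treatment?

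*Protocol*

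**What the plan says.** Protocol 3.5.2 is a list of circumstances for permanent discontinuation of study drug. One bullet reads "Any Grade 2 or higher cardiovascular or hematologic event", and its parenthesis continues "or Grade 3 lymphopenia or anemia as described below under" the Laboratory Criteria heading. That bullet carries no retest.

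The Laboratory Criteria further down the list work differently. After a listed value, "study drug should be paused, and an unscheduled visit (ie, sequential visit) should occur to retest within 3 to 7 days" (creatinine has a longer interval, and an earlier retest is allowed if medically indicated). Then: "If the laboratory abnormality is confirmed by the retest, then study drug should be permanently discontinued". The six listed values include "ANC < 1500 cells"/mm³, "Platelet count < 75,000 cells"/mm³ and "Hemoglobin < 8.0 g/dL".

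Four other places bear on the point:

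- Protocol 7.1.2.1 exempts asymptomatic laboratory abnormalities that are not clinically significant from being AEs. Protocol 7.6 nevertheless says that abnormalities that "lead to study drug interruption, modification, or discontinuation must be recorded as an AE".
- Protocol 7.2.2 and 7.6 grade laboratory-associated AEs by clinical severity, which need not match the laboratory grade.
- Protocol 3.5.1 requires discussion with the medical monitor before study drug is resumed. Appendix 6 mentions tests done to decide on resumption.
- Protocol 7.7 sends clinical toxicities to Section 3.5 and clinically significant laboratory toxicities to Appendix 5. The Appendix 5 chart is not visible in this copy; only a reference back to Section 3.5 and two footnotes can be read.

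**The concern.** Read together, these rules seem able to give one subject two different end actions. The pause ordered by the Laboratory Criteria is an interruption, so 7.6 turns the low count into a recorded AE. If that AE is graded 2 or higher, the hematologic-event bullet applies and treatment ends. If the retest is normal, the Laboratory Criteria do not call for a permanent stop. The parenthesis links only lymphopenia and anemia to the Laboratory Criteria, so neutrophils and platelets have no stated bridge between the two rules.

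The parenthesis also attaches a grade to laboratory values, whereas 7.2.2 grades on clinical severity, so a reader may wonder which grade the bullet means.

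At stake would be consistent handling across sites in a study whose primary objective is safety. The choice also reaches reported output: SAP 4.1 tabulates reasons for stopping study drug, and SAP 7.1.6 counts TEAEs leading to its discontinuation. Neutropenia is not hypothetical for this compound, since the first-in-human study had one Grade 3 case (Protocol 1.2.3.1).

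**Working it through.** The plan gives no figure to reproduce. The check is to apply both rules to each possible case of a low neutrophil or platelet count.

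| Case (ANC < 1500 or platelets < 75,000 cells/mm³) | Hematologic-event bullet | Laboratory Criteria | Conflict? |
|---|---|---|---|
| AE below Grade 2, retest normal | not met | no permanent stop | no |
| AE below Grade 2, retest confirms | not met | permanent stop | no; one criterion is enough |
| AE Grade 2 or higher, retest confirms | permanent stop | permanent stop | no |
| AE Grade 2 or higher, retest normal | permanent stop | no permanent stop | yes |

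Only the last row diverges. To reach it, a subject needs (1) a pause for a low count, (2) AE recording under 7.6, (3) an AE grade of 2 or higher on clinical severity and (4) a normal retest. Section 7.6 requires recording but assigns no grade, so step 3 does not follow from step 2.

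**Scope.** The Laboratory Criteria have six entries: hemoglobin, ANC, lymphocytes, platelets, AST/ALT and creatinine clearance. Hemoglobin and lymphocytes are bridged by the parenthesis, and AST/ALT and creatinine clearance are not hematologic. Two of six remain.

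**Treatment days for one affected subject.** The nominal visits in Appendix 3 are Week 1 = day 7, Week 2 = day 14 and Week 4 = day 28. Assume the result is known on the visit day, the pause lasts 3 to 7 days and dosing resumes on the retest day. Days left = 28 − visit day − pause.

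- Week 1 finding: 28 − 7 = 21; 21 − 7 = 14 to 21 − 3 = 18 days, or 14/28 = 50% to 18/28 = 64%. Under the event bullet: 0.
- Week 2 finding: 28 − 14 = 14; 14 − 7 = 7 to 14 − 3 = 11 days, or 7/28 = 25% to 11/28 = 39%. Under the event bullet: 0.

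These ranges are illustrative, not limits. An earlier retest is allowed, so the ceilings are 21 days (75%) and 14 days (50%). Each day spent waiting for a result or for the medical monitor discussion takes one day off.

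**Frequency.** The documents do not say how often a count is graded 2 or higher and then recovers within a week. The first-in-human neutropenia was recorded on Day 11 and again on Day 19, 19 − 11 = 8 days later, so it is not an example of the divergent case.

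**Effect on the analysis.** The primary endpoints count subjects with AEs and with laboratory abnormalities. The triggering AE and laboratory value are recorded and counted under either action. What can change is later exposure, events that depend on it, and the discontinuation counts. The SAP lists by participant the reasons for stopping study drug (4.1), drug administration (4.2.2), important protocol deviations (4.3) and treatment-emergent laboratory abnormalities (7.2.2.2). A reader of the report could reconstruct what was done.

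**The case for a change.** The best case for acting is that the gap is on the page and neither the AE exemption nor a specific-over-general reading closes it. Section 7.6 overrides the exemption as soon as drug is paused. A specific-over-general reading is weakened because the parenthesis names two blood counts and omits the other two on the same list. If all four were meant to go through the retest, the cross-reference is incomplete. If not, the retest has no effect for a neutrophil or platelet finding graded 2 or higher. A clarification would cost one sentence.

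That much stands as a remark on drafting. It does not show that the protocol leaves the case undecided:

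- The entries in 3.5.2 are separately sufficient. A subject who meets one is to be discontinued, and failing to meet another does not undo that.
- Nothing in 3.5.2 orders resumption after a normal retest. Possible resumption is inferred from 3.5.1, which makes it subject to discussion with the medical monitor, and from a note in Appendix 6 on where samples are sent.
- The grading basis for AEs is stated in 7.2.2, and SAP 7.1.2 names CTCAE v5.0. The parenthesis labels its own items as belonging to the Laboratory Criteria.
- The two Appendix 5 footnotes together name the same analytes as the Laboratory Criteria, and the second adds only hemoglobin and lymphocytes, the pair singled out in the parenthesis. This suggests a deliberate scheme by analyte and grade. It is not proof, because Appendix 5 also refers back to Section 3.5, but without the chart an omission cannot be demonstrated.

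**Conclusion.** No change to the plan follows. The hematologic-event bullet and the Laboratory Criteria are imperfectly joined for neutrophils and platelets, and the readable text states no order between them. The divergence is confined to one of four cases and two of six laboratory values, and decisions to pause, stop or resume already involve the medical monitor.

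For a single affected subject the difference could be a substantial part of the 28 days of treatment, but no frequency can be given. For the study, the effect is negligible. SAP Section 1 reports 3 enrolled participants, of whom 2 completed the study and 1 was terminated by the sponsor. SAP Section 8 drops the PK analysis, the remaining analyses are descriptive, and the planned listings would show any such episode. The documents report no hematologic stop among the 3, although completing the study does not by itself show that study drug was completed.

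This conclusion assumes that AE grades follow 7.2.2 and that the missing chart does not introduce a different rule. If the wording is carried into another protocol, the sponsor's clinical team must reconcile 3.5.2, 7.6, 7.7 and Appendix 5; which action should apply is theirs to decide.
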